#### **6.5 Cycle 1, Day 21: On-treatment Biopsy**

Fresh tumor sample collection will occur during cycle 1 at 3 weeks of cabozantinib therapy (between days 21 and 24 of treatment, inclusive).

**NOTE: Cabozantinib must be held 5 days before and 5 days after biopsy**

#### **6.6 Cycle 2, Day 1 + Cycle 3, Day 1**

- Physical Examination with vital signs and weight
- ECOG Performance Status
- CBC with differential and platelet count
- CMP (with direct bilirubin with known Gilbert's syndrome)
- Concomitant medications
- Skeletal-related events
- Adverse events
- Dispense/return oral study drug and compliance accounting

#### **6.7 Cycle 4, Day 1 +**

##### **Every 4 weeks ( $\pm$ 3 day(s))**

- Physical Examination with vital signs and weight
- ECOG Performance Status
- CBC with differential and platelet count
- CMP (with direct bilirubin with known Gilbert's syndrome)
- SOC and Research scans/labs to be collected as per schedule of assessments
- Skeletal-related events
- Adverse event evaluation
- Concomitant medications
- Dispense/return oral study drug and compliance accounting

#### **6.8 Treatment Administration**

Treatment will be administered on an outpatient basis. Reported adverse events and potential risks are described in Section 7. Appropriate dose modifications for cabozantinib are described in Section 7.

#### **6.9 End of Treatment**

Subjects will return to the study site approximately 30 days after their last dose of cabozantinib to complete end-of-study assessments.

- Physical Examination with vital signs and weight
- ECOG Performance Status
- CBC with differential and platelet count
- CMP (with direct bilirubin with known Gilbert's syndrome)
- Thyroid function tests
- PSA
- Testosterone
- LDH

- Concomitant medications
- Circulating Immune Activity sample
- cfDNA
- Skeletal-related events
- Adverse events
- Return oral study drug
- CT/MRI abdomen/pelvis (if not done within 6 weeks)
- CT chest (if not done within 6 weeks)
- Bone scan (if not done within 6 weeks)

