### 1.2.3 Exploratory Objectives

- To evaluate for and measure changes in targeted altered genes found in cell free DNA at baseline, in response to treatment, and at the time of disease progression.
- To explore the effects of cabozantinib on tumor immune microenvironment response through on-treatment biopsy and collection of plasma for analysis.
- To explore any relationship between baseline and on-treatment tumor genomic abnormalities (such as mutations, translocations, messenger ribonucleic acid [mRNA], protein expression and localization) with any observed antitumor activity.

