## **2.5 Correlative Studies Background**

### *Cell-free DNA*

Measurement of cell-free or circulating tumor DNA (ctDNA) in plasma is a noninvasive method to molecularly analyze and characterize a patients' tumor. In addition, it allows repeated longitudinal sampling. In the current study, we aim to define the spectrum and frequency of genomic changes found in plasma DNA of patients with mCRPC prior to cabozantinib therapy and determine types and frequencies of genomic mutations that arise with treatment. In collaboration with [name], we will collect plasma samples and then analyze them using the PCF SELECT (Specific Evaluation in Liquid biopsies of Established prostate Cancer Targets) plasma ctDNA assay. This is a custom designed prostate cancer specific panel including 74 target genes, 42 control genes covering both exonic regions and informative single nucleotide polymorphisms (SNPs) optimized for the detection of CRPC aberrations including estimation of copy number in ctDNA. PCF SELECT (tumor DNA from cfDNA and germline control) will be run at baseline, on therapy (at 3 months), and at clinical progression.

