 cfDNA, circulating immune activity, lipase can be collected within 30 days prior to C1D1 or pre-dose C1D1

 When plasma DNA is collected, it should be collected as close to biopsy date as possible, including same day. In the event it is collected on the same day, the specimen should be acquired *prior* to the biopsy procedure.

 Every 12 weeks (± 5 days) until disease progression. For EOT, does not have to be repeated if done within 6 weeks of visit.

 Assess continuously until disease progression

 Every 12 weeks beginning with C4D1 (e.g. C4, C7, C10, etc).

 Collect only on C4D1

 Pre-treatment biopsy can be waived provided that adequate archival material for molecular analyses available from biopsy performed within 3 months of enrollment

 On-treatment biopsy during cycle 1 after 3 weeks of therapy. Biopsy must be performed between day 21 and day 24 on therapy (inclusive). *NB: cabozantinib must be held 5 days before and 5 days after biopsy*

Cycle = 28 days	Screening	Cycle 1			Cycle 2	Cycle 3	Cycle 4 +	End of Treatment	Survival Follow-Up
	Day -30 to -1	Day 1	Day 14	Day 21 (+ 3 days)	Day 1 (± 3 days)	Day 1 (± 3 days)	Day 1 (± 3 days)	Post-Treatment	
Concomitant medications 	X	X			X	X	X	X	
Adverse events 	X	X	X		X	X	X	X	
Health Care Resources 	X	X			X	X	X	X	
Cabozantinib dosing 		X			X	X	X		
Dispense/return of oral study drug and compliance accounting		X			X	X	X	X	
Additional cancer treatment, survival status								X	Subjects will be followed every 12 weeks for 2 years after completion of the study or until death, whichever occurs first

 Document those taken from 30 days prior to treatment through 30 days after the decision to discontinue study treatment

 Document new or worsening events from time of informed consent through 30 days after the last dose of study treatment (related SAEs at any time). Adverse events information will be collected at study visits and may also be collected at any time over the phone or by spontaneous subject report. At study visits where any study treatment is administered, adverse events will be documented pre- and post-dose. Certain AEs and all SAEs that are ongoing 30 days after last dose of study treatment are to be followed until resolution or determination by the investigator that the event is table or irreversible.

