## 8.2 Prohibited or Restricted Therapy

The following therapies are prohibited until study treatment has been permanently discontinued:

- Any investigational agent or investigational medical device.
- Any nonprotocol systemic anticancer treatment (e.g. chemotherapy, immunotherapy, radionuclides, drugs or herbal products used specifically for the treatment of the cancer under investigation).
  - The following therapies should be avoided until study treatment has been permanently discontinued or until otherwise specified:
- Local anticancer treatment including palliative radiation, ablation, embolization, or surgery with impact on tumor lesions should not be performed until radiographic progression per RECIST 1.1 has been established.
- Erythropoietic stimulating agents (e.g. epoetin alfa and darbepoetin alfa) should not be used based on a report of increased risk of tumor recurrence/progression associated with erythropoietin (Wright et al 2007).
- Concomitant medications that are known to prolong the QTc interval should be avoided in subjects who receive cabozantinib until they have permanently discontinued cabozantinib treatment (refer to <http://www.qtdrugs.org> for a list of drugs which have the potential to prolong the QTc interval).
- Chronic co-administration of cabozantinib with strong inducers of the CYP3A4 family (e.g. phenytoin, carbamazepine, rifampin, rifabutin, rifapentine, phenobarbital, and St. John's

Wort) may significantly decrease cabozantinib concentrations and should be avoided. Selection of alternate concomitant medications with no or minimal CYP3A4 enzyme induction potential is recommended.

- Caution must be used when discontinuing treatment with a strong CYP3A4 inducer in a subject who has been concurrently receiving a stable dose of cabozantinib, as this could significantly increase the exposure to cabozantinib.
- Co-administration of cabozantinib with strong inhibitors of the CYP3A4 family (e.g. boceprevir, conivaptan, posaconazole, ketoconazole, itraconazole, clarithromycin, atazanavir, indinavir, nefazodone, nelfinavir, saquinavir, ritonavir, lopinavir, telaprevir, telithromycin, and voriconazole) may increase cabozantinib concentrations and should be avoided. Grapefruit, star fruit, and Seville oranges may also increase plasma concentrations of cabozantinib and should be avoided.
- Additional information on potential drug interactions with cabozantinib is provided in Section 8.3.

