## **9 CORRELATIVE/SPECIAL STUDIES**

### *i. Cell-free plasma DNA and archival tissue:*

Plasma samples for ctDNA will be collected for analysis prior to treatment (as close to biopsy timing as possible), at 12 weeks, and at progression using the PC specific platform developed in collaboration with [name]. We will also request archival paraffin embedded tissue to incorporate tissue-based and cell free DNA approaches to assess PC pathway changes and genomic /epigenomic alterations and will correlate with clinical response. We will evaluate the association of molecular biomarkers with treatment response.

We will also compare tumor tissue targeted genomic sequencing results (CLIA test used for inclusion) with ctDNA findings at baseline and determine their concordance, identify and track these alterations, monitor ctDNA tumor content and quantify relevant tumor clones on therapy, and analyze somatic

alterations that emerge at the time of progression/therapy resistance. We predict that a molecularly defined subset of CRPC will preferentially respond to Cabozatinib and this group is detectable using plasma-based assays. These data will help develop a non-invasive blood-based method for future trial inclusion criteria, as well as provide new insights into mechanisms of response/resistance to Cabozantinib in prostate cancer.

ii. *Immune Assays:*

Mandatory collection of 5 mL of plasma or serum in Serum Separation Tubes will be obtained at baseline, every 12 weeks, and at the time of disease progression. These will be aliquoted in 100 microliter fractions and stored at -80 degrees C prior to thaw for analysis.

iii. *Tumor Tissue:*

Metastatic tumor tissue biopsies will be taken with core needle or excisional biopsy. Fine needle aspiration is **not** allowed. It is encouraged that 6 core samples be collected from a single site with a minimum of 4 core samples collected. The biopsy sample will be split into two components, one formalin fixed for histological and immunohistochemical analyses, as well as possible DNA mutation analysis. The other component will be flash frozen for RNA isolation and sequencing. In addition to the typical hematoxylin and eosin staining for tumor morphology and histologic classification.

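### Three sections call for a cfDNA sample at progression, but the schedule ties no draw to progression; after C4D1 the only later tube comes about 30 days after the last dose

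*Combined protocol and SAP*

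**What the plan says.** Three places set the intended time points.

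- Section 1.2.3 sets out to measure changes in target genes "found in cell free DNA at baseline, in response to treatment, and at the time of disease progression".
- Section 2.5 says the plasma assay "will be run at baseline, on therapy (at 3 months), and at clinical progression".
- Section 9 collects plasma before treatment, then "at 12 weeks, and at progression using the PC specific platform". One stated use is to analyse "alterations that emerge at the time of progression/therapy resistance".

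The operational sections read differently. In the Section 6.1 table, cfDNA is marked at screening or C1D1, in the Cycle 4+ column and at End of Treatment. Footnote 9 restricts the Cycle 4+ entry: "Collect only on C4D1". Section 6.9 lists cfDNA among the End of Treatment procedures and times that visit: "Subjects will return to the study site approximately 30 days after their last dose of cabozantinib to complete end-of-study assessments". Footnote 6 says of the scans: "For EOT, does not have to be repeated if done within 6 weeks of visit".

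Section 8.2 limits other systemic anticancer treatment only while the patient is on study drug: "The following therapies are prohibited until study treatment has been permanently discontinued". The End of Treatment column of the schedule has an entry for recording additional cancer treatment.

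**The concern.** A sample meant to show what has emerged under drug pressure should be taken while the patient is on drug, or as near to documented progression as practicable, and before another agent is given. The schedule has no visit defined by progression, and footnote 9 rules out a scheduled cfDNA draw at C7, C10 and later, which are the visits where 12-weekly scans would show it. A site working from the table would take its last cfDNA tube at End of Treatment.

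At stake is the interpretation of the baseline-to-progression comparison. If the third tube comes from a mixture of times and circumstances (weeks off drug, possibly on a new agent, or after stopping for toxicity), a difference from baseline cannot be attributed with confidence to resistance to cabozantinib. With at most 30 patients, few samples are available to absorb that ambiguity, and a tube not drawn at progression cannot be recovered afterwards.

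**Working it through.** The plan gives no figure to reproduce here. The check sets the schedule against the stated time points, then sizes the delay.

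**Step 1. Where the scheduled draws fall.** Cycles are 28 days, so C4D1 is day 3 × 28 + 1 = 85 and C7D1 is day 6 × 28 + 1 = 169. Scans are every 12 weeks (footnote 6).

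| When progression is found | Scheduled cfDNA near it | Later scheduled cfDNA |
|---|---|---|
| Before C4D1, drug stopped | none on treatment | End of Treatment |
| At the 12-week scan | C4D1 tube may be close | End of Treatment |
| At C7, C10 or later | none (footnote 9) | End of Treatment |
| After stopping for toxicity | none | none; the End of Treatment tube normally comes before progression |

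**Step 2. Bone progression.** Section 10.4 asks that bone progression at the first scheduled assessment be confirmed 6 or more weeks later unless soft tissue or symptoms are clearly worsening. Counting from day 85, that is day 85 + 42 = 127 or later. No cfDNA draw is scheduled at that point, and the plan does not say which of the two scans would define the progression sample.

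**Step 3. Delay from progression to the tube.** Radiographic progression ends treatment (Sections 3.1 and 7.10). If dosing stops when progression is documented, the End of Treatment tube is about 30 days late. Scans up to 6 weeks (42 days) old need not be repeated, so the tube can be up to 42 days after the scan with no newer imaging beside it.

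**Step 4. Drug remaining at the tube.** The protocol text gives no half-life. Section 7.9.2 gives steady state at about 2 weeks. Assume that this represents k half-lives, with k from 3 to 5, and first-order elimination:

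- half-life = 14 / k days
- fraction remaining at 30 days = 0.5^(30 / half-life)

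| k | Half-life (days) | Remaining at 30 days |
|---|---|---|
| 3 | 4.67 | 1.16% |
| 4 | 3.50 | 0.26% |
| 5 | 2.80 | 0.06% |

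Because the visit time is approximate, the same formula at 25 and 35 days gives an outer range of 2.4% (k = 3, day 25) to 0.02% (k = 5, day 35).

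**Step 5. New therapy before the tube.** The bar in Section 8.2 lifts at permanent discontinuation, about 30 days before the visit. No section requires the draw to precede the next treatment. Starting a new agent in that window is therefore possible; the documents do not say how often it would happen.

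**The case against.** The strongest reply is that the plan already states the right time point. Section 9 says plasma is collected at progression, a site could act on that, and handling instructions sit in a Lab Manual that is not part of these documents. Nothing calls the End of Treatment tube the progression sample. This stands in part: the intention is clear, so the fault is an inconsistency and not a deliberate choice of a late draw. It does not remove the problem, because no visit or footnote carries the intention out and footnote 9 points the other way.

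It is also fair that the C4D1 tube may serve for progression found at the 12-week scan, so the gap falls mainly on patients who progress later.

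A reader might infer more than the documents support:

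- *That the drug is gone by End of Treatment.* This rests on an assumed half-life; that most has probably cleared is as far as it goes.
- *That some patients will already be on another agent.* The plan permits it and records it, but gives no frequency.
- *That toxicity stops are pooled as progression.* No section says so. Section 12.4 simply gives no rule to keep them apart.
- *That a resistant subclone will shrink off drug, or that a new agent will change the clone mix by day 30.* Nothing in the documents establishes either.
- *That about 71% of patients are affected.* Putting the 5.6-month COMET-1 median through an exponential curve gives 0.5^(2.76/5.6) = 71% event-free at 12 weeks. That trial enrolled unselected men with bone-dominant disease, and this one selects on molecular targets or liver metastases, so the share here is unknown.

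**Conclusion.** The point holds as an internal inconsistency confined to one exploratory objective. Sections 1.2.3, 2.5 and 9 require a progression sample; Section 6.1 (footnote 9) and Section 6.9 do not schedule one. For patients who progress after C4D1 the only later tube is about 30 days after the last dose, possibly after new treatment, with roughly 0.06% to 1.2% of drug remaining under the 3-to-5 half-life assumption. The inconsistency itself needs no assumption and can be read from the schedule. The number of patients affected cannot be derived from the documents.

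The baseline and 12-week cfDNA aims, the tissue-to-plasma concordance aim, and the rPFS, response, PSA, survival and safety analyses are untouched. It is worth correcting in the next amendment because the fix is cheap and a missed sample is lost for good; it does not threaten the trial's main conclusions.

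**What to change.** Reconcile footnote 9 and Section 6.9 with Section 9:

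1. Schedule the third cfDNA tube at the visit where radiographic progression is documented, before any new anticancer therapy. The wording should govern the timing of the research tube only, not that of the patient's next treatment.
2. For bone progression that needs confirmation under Section 10.4, state which scan triggers the draw.
3. Keep the End of Treatment draw as the fallback when the progression tube was missed or the patient stopped without progression.
4. Record the dates of the draw, the last dose and the start of any new therapy with every third tube.
5. State in Section 12.4 that End of Treatment samples from patients without progression are analysed separately from the progression and resistance comparison.

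The cost is wording in the schedule, Section 6.9, Section 12.4 and the Lab Manual, plus three dates on the form. The number of tubes and assays per patient stays the same, since End of Treatment becomes the alternative and not an addition. Some patients may need a short return visit once the scan is read. A patient who stops for toxicity and progresses later would still have no progression tube; if one is wanted, it is an extra draw, because survival follow-up schedules no blood sampling, and the protocol should say so.

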### **7.10 Duration of Therapy and Criteria for Removal from Study**

Subjects may discontinue study treatment or withdraw their consent to participate in the study at any time without prejudice. The investigator may withdraw a subject from study treatment or from the study if, in his or her clinical judgment, it is in the best interest of the subject or if the subject cannot comply with the protocol.

In addition, any of the following conditions require discontinuation of the subject from study treatment:

- An AE or intercurrent illness that in the opinion of the investigator warrants the subject's withdrawal from study treatment;
- The investigator believes it is not in the best interest of the subject to continue on study
- Specific conditions described in the Management of Adverse Events Section;
- Necessity for treatment with other anticancer treatment prohibited by protocol;
- Sexually active subjects who refuse to use medically accepted barrier methods of contraception (e.g., male condom, female condom) during the course of the study and for 4 months after discontinuation of study treatment;

- If the subject does not recover from his or her toxicities to tolerable Grade  $\leq 2$  within 6 weeks, the subject will have study treatment discontinued unless there is unequivocal evidence that the subject is benefitting. In this situation, a subject may be able to restart therapy with a dose reduction upon resolution of the toxicity and with agreement of the principal investigator / Sponsor;
- Request by regulatory agencies for termination of treatment of an individual subject or all subjects under the protocol;
- Significant noncompliance with the protocol schedule in the opinion of the investigator;
- Subjects who cannot tolerate the minimum protocol-specified dose of study treatment will have study treatment discontinued;
- Progressive disease (PD) or the subject no longer experiences clinical benefit as determined by the investigator

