### **10.1 Response Criteria**

In order to evaluate efficacy, all study-required tumor assessments and PSA measurements must be obtained. Baseline and all post baseline PSA assessments will be used to measure PSA response rate and time to PSA progression based on protocol-specific/modified PCWG3 criteria. Any unscheduled PSA measurement will be included in the periodic assessment of PSA progression.

Radiographic scans (CT, MRI, or bone) will be used to assess best overall response and radiographic progression based on PCWG–modified RECIST criteria for soft-tissue lesions and protocol-specific criteria for bone lesions. Baseline images should be taken during Screening as close as possible to, and never more than 28 days before, Day 1 Week 1. Every effort must be made to ensure the same radiographic method is used before and after treatment at scheduled visits.

Other disease-related signs or symptoms suggestive of progression, including escalating pain not referable to another cause, increased LFT in subjects with baseline liver metastases, increased ascites, declining performance status, and examination findings consistent with disease progression, are valid reasons to consider an unscheduled assessment of tumor status.

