### 10.3 PSA

As long as patient safety is the primary concern, in the absence of other indicators of disease progression, therapy should not be discontinued solely on the basis of a rise in PSA.

For each patient, a waterfall plot will be used to report the percent change in PSA from baseline to 12 weeks (or earlier for those who discontinue therapy) and the maximum decline in PSA that occurs at any point after treatment

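### A PSA fall on the next anticancer drug can be scored as a cabozantinib response: every post-baseline PSA counts, and the end-of-treatment sample comes about 30 days after the last dose

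*Combined protocol and SAP*

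**What the plan says.** **Timing of the last PSA.** Section 6.9: "Subjects will return to the study site approximately 30 days after their last dose of cabozantinib to complete end-of-study assessments". PSA is listed there with no waiver. CT/MRI and bone scan are listed too, but conditionally; the footnote in section 6.1 reads "For EOT, does not have to be repeated if done within 6 weeks of visit".

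**When other therapy is allowed.** Section 8.2: "The following therapies are prohibited until study treatment has been permanently discontinued". The list that follows includes "Any nonprotocol systemic anticancer treatment". Section 7.10 gives as one reason for stopping cabozantinib "Necessity for treatment with other anticancer treatment prohibited by protocol". The schedule in section 6.1 has a row "Additional cancer treatment, survival status", marked at end of treatment and continued into survival follow-up.

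**Which values count.** Section 10.1: "Baseline and all post baseline PSA assessments will be used to measure PSA response rate and time to PSA progression". Section 10.3 asks for a waterfall plot of two quantities. One is the change to week 12, cut short for men who stop treatment. The other is "the maximum decline in PSA that occurs at any point after treatment". Section 12.3.2 reports the proportions with 30% and 50% PSA declines, each with a binomial interval, and sets no time window. For scans, section 10.1 says only that they serve to assess best overall response and radiographic progression.

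**The concern.** A response proportion in a single-arm trial is read as the effect of the study drug. That reading fails if the values that decide response include some taken while the man was on a different active drug. Here the PSA rule is explicitly inclusive, the last scheduled PSA falls after the ban on other therapy has ended, and no analysis rule uses the record of new therapy. The 30% and 50% PSA decline proportions could therefore include men whose PSA fell on the next treatment. There is no control arm in which the same error would appear and cancel.

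**Working it through.** The plan states no expected value or precision for PSA or tumor response. Its only precision figure (section 12.1, 31.1-68.9%) concerns rPFS and plays no part here. The check is a comparison of the rules, followed by the effect of one misclassified man.

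**1. The rules in time order**

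| Point in time | Rule | Section |
|---|---|---|
| Permanent discontinuation | Ban on other systemic anticancer therapy ends | 8.2 |
| About 30 days after last dose | PSA drawn, no waiver | 6.9, 6.1 |
| Same visit | New cancer treatment recorded | 6.1 |
| Analysis | All post-baseline PSA used; maximum decline has no end date | 10.1, 10.3 |
| Analysis | 30% and 50% decline proportions, no rule on new therapy | 12.3.2 |

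A new drug can therefore precede the last PSA by up to about 30 days, and that PSA counts.

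**2. Direction**

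Let m1 be the lowest PSA/baseline ratio before any new therapy and m2 the lowest ratio after it. As written, a 50% response is min(m1, m2) ≤ 0.5; with a cut-off it is m1 ≤ 0.5. Because min(m1, m2) ≤ m1, the uncut rule can add responders and cannot remove any. The same holds at 0.7 for the 30% decline.

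**3. Size per man**

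N = 30 (section 12.2), so one man is 1/30 = 3.3 points. Exact (Clopper-Pearson) 95% intervals:

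| Responders | Proportion | 95% CI |
|---|---|---|
| 2/30 | 6.7% | 0.8-22.1% |
| 3/30 | 10.0% | 2.1-26.5% |
| 4/30 | 13.3% | 3.8-30.7% |

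**4. Expected number**

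Expected excess = 30 × (1 − p) × f × q, where
- p is the true PSA response rate on cabozantinib;
- f is the share of non-responders who start a new drug before the end-of-treatment PSA;
- q is the chance that such a man is at least 50% below study baseline by then.

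The documents give neither f nor q, so the excess cannot be computed. A break-even can. Taking p = 6% as an illustration (the COMET-1 PSA response quoted in section 2.2.1), an expected excess of one man needs f × q = 1/(30 × 0.94) = 0.035.

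**5. How much weight the last PSA carries**

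After Cycle 1 Day 1, PSA is next scheduled at Cycle 4 Day 1, which is day 3 × 28 + 1 = 85, and every 12 weeks after that. For a man who stops before day 85, the end-of-treatment PSA is the only scheduled one after Cycle 1 Day 1. Section 12.5.2 requires three cycles (84 days) for response evaluation but does not say whether this covers PSA. Men treated longer are affected either way.

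**6. Scans**

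The waiver covers scans within 6 weeks (42 days) of the visit. With a day-30 visit, a scan done up to 42 − 30 = 12 days before the last dose removes the need for another. A man who stops on a fresh progression scan will therefore usually have no end-of-treatment scan. What remains is mainly men who stop for toxicity or another reason with an older last scan. For them, best overall response has no stated cut-off.

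**The case against.** The strongest case on the other side has four parts.

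- **The text is less open than it looks.** Section 10.3 does shorten the 12-week change for men who stop, and its maximum-decline phrase describes a waterfall plot, not the responder definition in section 12.3.2. This is correct, but the shortening covers only the 12-week change. Section 12.3.2 has no window of its own, which leaves the inclusive sentence in section 10.1 to govern PSA response.
- **PCWG3 may already limit which values count.** Section 10.1 refers to protocol-specific or modified PCWG3 criteria, which are not reproduced, so this cannot be checked from the documents. The protocol does state its own inclusive rule, and an unstated default should not be relied on to override it.
- **The event is demanding.** A falsely credited man must start a new drug and be at least 30% or 50% below his study baseline within at most about 30 days, often after progressing. This stands. The number may be below one man, and the intervals for 2/30 and 3/30 overlap heavily.
- **No decision depends on it.** PSA decline is a secondary estimate with no null value or threshold. This also stands.

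Some stronger readings are tempting but unsupported. A reader might infer that the same inclusive rule covers scans; the wording in section 10.1 applies to PSA only. A reader might take the 6% from COMET-1 as a benchmark that one or two men would overturn; it is background, and section 12 does not use it. A reader might take the row for additional cancer treatment as showing that the plan expects men to be on a new drug by the visit, or that start dates are already collected. The row also serves survival follow-up, and it names no date.

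**Conclusion.** The PSA rule is wrong as written. Followed literally, it credits cabozantinib with a PSA fall that occurs on the next drug, and the bias in the 30% and 50% decline proportions can only be upward. Each such man is worth 3.3 points, assuming all 30 men are in the denominator. The number of such men cannot be known from the documents and may be small.

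This conclusion rests on three readings: that section 10.1 governs the proportions in section 12.3.2, that the uncited detail of PCWG3 does not override it, and that at least some men start new therapy before the end-of-treatment visit. The protocol permits the last of these but does not predict it.

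For tumor response the documents support only a lesser concern: silence about a cut-off, in a subset of men without a recent scan. It deserves the same sentence because section 1.2.1 makes radiographic response the primary objective, although section 12.1 lists tumor response as secondary.

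**What to change.** 1. In sections 10.1, 10.3 and 12.3.2, state that PSA values obtained after the start of any new anticancer therapy are not used for PSA decline. For consistency, state that scans obtained after that point are not used for best overall response.
2. Add a start date to the additional-cancer-treatment item already in the schedule, so that the rule can be applied.
3. State the denominator. A man left with no usable post-baseline PSA should stay in as a non-responder, so that the cut-off does not shrink the denominator.
4. Report the uncut result as a sensitivity analysis.

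The cost is a few sentences of protocol wording and one date field. The response figures may be slightly less favorable, and some end-of-treatment values will go unused for response. No extra visit is needed, and nothing changes in when men may start other treatment.
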